9.9. ASTHMA EVALUATION

Asthma evaluation will be performed for subjects with asthma in Treatment Pathways 4 and 5 at visits according to the schedules of events in the appendices of the protocol. The evaluation of asthma severity will be assessed based on National Heart, Lung, and Blood Institute (NHLBI) classification (adapted from NHLBI, 2007).

Listing of the asthma evaluation results will be provided sorted by treatment pathway, subject ID, and visit.

9.10. TOTAL NASAL SYMPTOM SCORE

The TNSS (short form) will be administered only to subjects with known allergic rhinitis at the visits indicated in the schedules of events in the appendices of the protocol.

It consists of 3 questions that address nasal obstruction, rhinorrhea, and nasal itch/sneezing. Each question has a choice of 4 responses that range from 0 (no symptoms) to 3 (severe symptoms). The subject is asked to recall symptoms over the last week to allow calculation of the symptom score.

TNSS results will be listed by treatment pathway, subject ID, and visit.

9.11. STUDY TREATMENT EXPOSURE

The calculation of exposure will be based on in clinic dosing data and at home dosing as captured on the Study Product Exposure CRF page.

First and last dose dates for each study period are identified as described in Section 7.5.

The total amount of study product consumed will be calculated as the sum of in-clinic doses plus the estimated number of doses taken at home. At-home doses will be estimated by combining the doses across each dosing interval entered on the Study Product Exposure CRF page and taking into account the dosing frequency and any missed and partial doses as captured on the Subject Dosing Diary CRF.

The following calculations of study drug exposure will be made and summarized:

• Duration of Exposure (in days and in years): calculated as the date of last dose of study drug minus the date of the first dose of AR101 plus one during the study

> period, except for the Initial Escalation period, where the duration of exposure will only be 1 or 2 days depending on whether drug was taken on Initial Escalation Day 1 and Initial Escalation Day 2. Duration of exposure will be summarized using descriptive statistics for continuous data as well as categorically by 28-day increments for the first year and by year for the overall treatment periods: \leq 28 days, 29 to 56 days, 57 to 84 days, ..., 1 to < 2 years, 2 to < 3 years, 3 to < 4 years, 4 to < 5 years, and \geq 5 years.

- Total dose consumed (mg): calculated as the cumulative sum of all doses taken during the study period.
- Average dose per day (mg): calculated as the total dose consumed divided by the number of days during the study period.
- Maximum dose achieved (mg/day): summarized using descriptive statistics for continuous data as well as categorically using all possible dose levels: 0.5, 1, 1.5, 3, 6, 12, 20, 40, 80, 120, 160, 200, 240, or 300 mg/day.
- Number of unsuccessful dose increases: calculated as the number of single doses given at the study site at a higher dose level followed by an immediate return to the previous dose level or a lower dose level.
- Number of dose reductions: calculated as the number of any decrease in dose level given at the study site that does not qualify as an unsuccessful dose increase.

Study treatment exposure parameters will be summarized by the following study periods:

- Initial Escalation
- Up-Dosing
- Initial and Extended Maintenance
- Overall (ARC008 Only: Initial Escalation, Up-Dosing, and Initial and Extended Maintenance)

Duration of exposure will also be summarized including parent studies (Overall [Including Parent Studies]).

All ARC008 exposure data from the Dose Administration, Study Product Exposure, Missed and Partial Doses Log, and Subject Dosing Diary CRFs will be included in the subject listings.

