3.2.2 Initial Escalation Period (Treatment Pathways 3 and 5)

All Initial Escalation Period doses will be administered by study site personnel under direct observation in the clinic.

Initial dose escalation may be affected by a pandemic, epidemic, or other emergency not related to the study as described in Appendix 12.

Treatment Pathway 3

Eligible subjects will initiate AR101 at a dose of 0.5 mg of AR101 and then increase the dose incrementally at 20- to 30-minute intervals over the course of a single day to a maximum dose of 6 mg, according to the schedule in Table 2.

Table 2: Initial Escalation Schedule (Subjects Who Received Placebo in the Prior Study [Except ARC005])

Day 1 Dose Number	AR101 Dose, mg ^a	Cumulative AR101 Dose, mg ^a
1	0.5	0.5
2	1	1.5
3	1.5	3
4	3	6
5	6	12
Day 2 Dose Number	AR101 Dose, mg ^a	Cumulative AR101 Dose, mg ^a
1	3	3

Note: Doses will be delivered at 20 to 30 minute intervals under direct observation.

^a All mg doses shown refer to milligrams of peanut protein.

Subjects who do not tolerate ≥ 3 mg dose on Day 1 will discontinue dosing and complete the End of Treatment visit.

Subjects who tolerate ≥ 3 mg dose on Day 1 will undergo confirmatory dosing of a single 3 mg dose on the following day, Day 2. Subjects who tolerate this confirmatory dose will enter the Up-Dosing Period. Subjects who do not tolerate this confirmatory dose will discontinue dosing and complete the End of Treatment visit.

Treatment Pathway 5

Eligible subjects will begin initial dose escalation on Day 1 with a stepwise dose escalation of AR101 (up to 4 single doses of 0.5, 1, 1.5, and 3 mg) administered at 20- to 30-minute intervals as tolerated (Table 3).

Subjects who tolerate the 3 mg dose on Day 1 will return on Day 2 for a single 1 mg dose. Subjects who tolerate the 1 mg dose with no more than mild allergy symptoms that are not dose-limiting will begin the Up-Dosing Period. Subjects who do not tolerate any dose on Day 1 or Day 2 will discontinue dosing and complete the End of Treatment visit.

Table 3: Initial Escalation Schedule for Subjects Who Received Placebo in Study ARC005

Day 1 Dose Number	AR101 Dose (mg)	Cumulative Dose (mg)
1	0.5	0.5
2	1	1.5
3	1.5	3
4	3	6
Day 2 Dose Number	AR101 Dose (mg)	Cumulative Dose (mg)
1	1	1

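### SAP 9.11 counts the scheduled Day 1 to Day 2 step-down in Initial Escalation as an unsuccessful dose increase, even when every dose was tolerated

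*SAP*

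**What the plan says.** SAP 9.11 (Study Treatment Exposure) lists two counts among its exposure calculations. The first, unsuccessful dose increases, is the "number of single doses given at the study site at a higher dose level followed by an immediate return to the previous dose level"; the definition then extends to a return to any lower level. The second, dose reductions, takes in "any decrease in dose level given at the study site that does not qualify as an unsuccessful dose increase". Neither mentions tolerability, and neither exempts a planned change of dose.

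The same section treats the Initial Escalation doses as dose levels, listing "all possible dose levels: 0.5, 1, 1.5, 3, 6, 12, 20, 40" and so on up to 300 mg/day. It also states that "Study treatment exposure parameters will be summarized by the following study periods", and the list that follows includes Initial Escalation and an Overall summary. Table 4 in SAP 7.4 runs the Initial Escalation period through the latest Day 1 or Day 2 clinic dose, so both days fall inside it.

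Protocol 3.2.2 says that "All Initial Escalation Period doses will be administered by study site personnel under direct observation in the clinic". In Pathway 3 the dose rises "over the course of a single day to a maximum dose of 6 mg", and subjects who tolerate at least 3 mg "will undergo confirmatory dosing of a single 3 mg dose on the following day, Day 2". For Pathway 5, "Subjects who tolerate the 3 mg dose on Day 1 will return on Day 2 for a single 1 mg dose".

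**The concern.** The counting rule recognises a failed escalation by its footprint: a single clinic dose at a higher level, then a drop back. In Initial Escalation the protocol plans that footprint for subjects who are doing well. The count then loses its meaning for this period. A Pathway 3 subject who tolerates everything through 6 mg scores worse than one who got no further than 3 mg, and scores the same as one who took 6 mg, did not tolerate it and went on to the Day 2 dose.

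What is at stake is the reading of one row in the exposure tables. A line labelled as unsuccessful dose increases would report failures that did not happen, first for Initial Escalation and then again within Overall. SAP 6.1 says that summary tables generally combine the pathways into a single AR101 group, so a reader of the summary may be unable to remove the artefact.

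**Working it through.** The plan gives no expected value for this count, so there is no figure to reproduce.

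**Inputs.** Protocol Table 2 (Pathway 3) gives Day 1 doses of 0.5, 1, 1.5, 3 and 6 mg, then 3 mg on Day 2. Protocol Table 3 (Pathway 5) gives 0.5, 1, 1.5 and 3 mg, then 1 mg on Day 2. As a check, the Day 1 doses sum to 12 mg and 6 mg, matching the cumulative doses in those tables.

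**Rule as written.** Let d(i) be the i-th dose given at the site.
- Unsuccessful increase: d(i) > d(i−1) and d(i+1) ≤ d(i−1).
- Dose reduction: any other case with d(i+1) < d(i).

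For a fully tolerant Pathway 3 subject, 6 > 3 and the next dose, 3, is ≤ 3, so the count is 1. For a fully tolerant Pathway 5 subject, 3 > 1.5 and the next dose, 1, is ≤ 1.5, so the count is 1.

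| Course in Initial Escalation | Doses (mg) | Unsuccessful increases | Dose reductions |
|---|---|---|---|
| Pathway 3, all tolerated | 0.5, 1, 1.5, 3, 6, then 3 | 1 | 0 |
| Pathway 3, 6 mg not tolerated, Day 2 dose given | 0.5, 1, 1.5, 3, 6, then 3 | 1 | 0 |
| Pathway 3, stops at 3 mg on Day 1 | 0.5, 1, 1.5, 3, then 3 | 0 | 0 |
| Pathway 5, all tolerated | 0.5, 1, 1.5, 3, then 1 | 1 | 0 |
| Pathway 5, 3 mg not tolerated, dosing stopped | 0.5, 1, 1.5, 3 | 0 | 0 |

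**Carry-over into Overall.** Up-Dosing starts at 3 mg in Pathway 3 and 1 mg in Pathway 5, the same level as the Day 2 dose. An uneventful rising series adds nothing to either count, so Overall keeps the spurious 1.

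**Excluding the step from one count only.** If it is left out of unsuccessful increases alone, the residual definition of dose reductions picks it up, and the tolerant subject moves from (1, 0) to (0, 1). Excluding it from both counts gives (0, 0) in both pathways.

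**How many subjects.** Only former placebo subjects enter Initial Escalation. From the protocol's randomisation figures (sections 1.2.3 to 1.2.5):
- ARC007: 506 at 2:1, so 506/3 = 168.7 on placebo.
- ARC010: 175 at 3:1, so 175/4 = 43.8.
- ARC005: about 132 at 2:1, so 132/3 = 44.

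The sum is 168.7 + 43.8 + 44, or about 256. This assumes that all of them rolled over and received the last Day 1 dose. The documents give neither rollover numbers nor the share reaching 6 mg.

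**The case against.** The strongest reply is that the label itself says *unsuccessful*, and that the wording fits the up-dosing procedure in Protocol 6.9.3, where a first dose at a new level that is not tolerated is followed next day by the last tolerated dose. The protocol calls the Pathway 3 Day 2 dose confirmatory, and a sensible programmer might leave it out. That is possible, but the text does not lead there. SAP 9.11 reports the parameter for Initial Escalation, and it writes an explicit exception for that period under duration of exposure but none here. Timing does not separate the two cases either, since a real up-dosing failure also steps down the next day. A programmer who left the step out of the first count would still meet the residual definition of dose reductions.

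The handling may also sit in documents not available here: the separate table shells, or the tracking documents mentioned in SAP 7.7. This stands. The point is about the SAP text, and whether the final tables carry the artefact cannot be known from it.

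Three stronger readings are tempting, and the documents do not support them.
- A reader might infer that the primary safety and tolerability result is distorted. The count is listed as an exposure calculation and is absent from the endpoints in SAP 3.1 to 3.3.
- A reader might infer that reactions to 6 mg are hidden. Only this one count is blind to them: adverse events, anaphylaxis and rescue medication are each summarised for Initial Escalation, and the dose administration data are listed.
- A reader might divide 256 by 950 and report 27% of subjects. The 950 is a potential enrolment and the 256 assumes full rollover, so the ratio is not a usable estimate.

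**Conclusion.** The point holds for the SAP as written. The rule gives a wrong value for every Pathway 3 subject who tolerates 6 mg on Day 1 and receives the scheduled 3 mg on Day 2, and for every Pathway 5 subject who tolerates 3 mg on Day 1 and receives the scheduled 1 mg on Day 2: a count of 1 where 0 is true. Pathways 1, 2 and 4 have no Initial Escalation and are untouched.

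The consequence is limited to two summaries, Initial Escalation and Overall, of a descriptive parameter that feeds no endpoint, test or decision. The number affected is somewhere up to about 256. The conclusion rests on the published SAP text being what was programmed. It is worth correcting because this is a stated rule that yields a wrong number, and the correction is cheap.

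**What to change.** State that the protocol-scheduled change from the last Day 1 dose to the Day 2 dose in Initial Escalation is excluded from both the unsuccessful-increase count and the dose-reduction count, in the Initial Escalation and the Overall summaries. Leave the rule unchanged from the start of Up-Dosing.

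If tolerability is recorded dose by dose, Day 1 doses that were not tolerated may be shown as a separate line, so that two definitions are not added together in Overall. The documents do not show that such a field exists. If it does not, do not report these two counts for Initial Escalation, and still keep the scheduled step out of Overall.

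The natural place is SAP 9.11. However, SAP 1.1 says that Version 2 was made after database lock and is restricted to Appendix A, and SAP 6.1 expects amendments before lock. The practical route may therefore be a documented change in the clinical study report. The cost is a small programming change and a recorded post-lock departure. The exclusion itself uses doses and dates already collected and changes nothing in how subjects are treated.

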9.12. PRIOR, CONCOMITANT, AND RESCUE MEDICATIONS

All medications recorded on the Concomitant Medications CRF page for ARC008 will be coded using the World Health Organization international drug classification dictionary (WHODrug) Global C3 March 2023 version. Medications for all parent studies were coded using WHODrug 01 Mar 2013 for ARC002, WHODrug June 2015 for ARC003, and World Health Organization Drug Dictionary Enhanced (WHO-DDE) September 2016 for ARC004, ARC005, ARC007, ARC010, and ARC011. Medications were not coded for ARC001 and will not be included in medication summaries but will be included in the data listing of prior and concomitant medications. Medications will be listed and summarized by Anatomical Therapeutic Chemical (ATC) level 4 and preferred name. If ATC drug class level 4 is not available, then ATC drug class level 3 will be utilized. If ATC drug class levels 4 and 3 are not available, then ATC drug class level 2 will be utilized. If ATC drug class levels 4, 3, and 2 are not available, then ATC drug class level 1 will be utilized.

Prior medications are defined as those which are only taken prior to the date of the first dose of AR101 including parent studies (i.e., medication end date is prior to the date of first dose of study drug).

Concomitant medications are medications taken at any time during the active treatment period. Any medications recorded for which dosing began after the last dose of study treatment will also be classified as concomitant medications. As needed (PRN) medications, which may or may not be taken for long periods of time, but which are prescribed to the subject for a period that overlaps with the active treatment period, will be considered concomitant medications. If it cannot be determined whether a medication was received prior to the start of study drug dosing due to partial or missing medication start and/or end dates, it will be considered a concomitant medication.

Rescue medications are any medication used to treat individual acute allergic reactions during ARC008 should be according to recognized standards of care for allergy practice. In general, this could include either an antihistamine or epinephrine, along with intravenous fluids, a beta-adrenergic agonist (eg, albuterol), oxygen, or steroids, as indicated.

Prior medications, concomitant medications, and rescue medications will be summarized separately by ATC Class and generic drug name. Summaries of prior and concomitant medications will include medications from parent studies (ARC002, ARC003, ARC004, ARC005, ARC007, ARC010, and ARC011). Subjects will be counted no more than one time per generic drug name and no more than one time per ATC Level 4.

Rescue medications will be summarized by ATC Class and generic drug for the following study periods:

• Initial Escalation

- Up-Dosing
- Initial and Extended Maintenance (excluding rescue medications taken as a result of an OLFC)
- OLFCs (Total AR101 Exposure < 1 year; 1 to < 2 years; 2 to < 3 years; 3 to < 4 years; 4 to < 5 years; ≥ 5 years)
- DBPCFCs (Total AR101 Exposure < 1 year; 1 to < 2 years; 2 to < 3 years; 3 to < 4 years; 4 to < 5 years; ≥ 5 years)
- Overall, including all rescue medications reported on the CRF

The summary of rescue medications will be repeated for the subgroups described in Section 6.3.

Prior medications and concomitant medications (including medications from parent studies [ARC001, ARC002, ARC003, ARC004, ARC005, ARC007, ARC010, and ARC011]), prior and on-study rescue medications, prior and on-study epinephrine, and concomitant non-drug therapies will be listed by subject.

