7.1.3 End of Treatment Visit

At the early discontinuation of AR101 dosing (for subjects who discontinue early) or at the end of AR101 treatment, subjects will return to the clinic for the End of Treatment visit. A DBPCFC (Appendix 11) will be performed for all subjects except those who discontinue early for safety reasons. AR101 will not be administered on the days of the DBPCFC. AR101 dosing will continue until the last food challenge is performed.

The following procedures will be performed before the DBPCFC:

- Monitoring and recording of AEs, including allergic symptoms
- Concomitant medication review
- Food allergen exposure update
- Return of unused AR101
- AR101 dosing compliance check
- Complete physical examination, including weight and height
- Vital signs
- PEF (should be measured at approximately the same time of day at each visit assessment)
- Blood sample collection:
 - CBC (if not completed within prior 6 months)
 - Immunology assessments
- Urine pregnancy test (for sexually active females of childbearing potential only)
- SPT
- PEESS v2.0 (for subjects who had GI AEIs)

- Completion of questionnaires:
 - ACT/C-ACT (for subjects with known asthma only) (before PEF assessment)
 - TNSS (for subjects with known allergic rhinitis only)
 - FAQLQ and FAIM

The following procedures will be performed before discharge from the clinic:

- Monitoring and recording of AEs, including allergic symptoms
- Peanut allergy training

At the end of the End of Treatment visit, the investigator must advise the subject or parent/caregiver of appropriate options for continued management of peanut allergy.

Telephone contact: Site staff will contact the subject or subject's parent/caregiver by telephone at least 14 days after the last AR101 dose or last food challenge, whichever is last, to enquire if any AEs (including allergic symptoms, GI symptoms, and accidental/nonaccidental food allergen exposure) occurred after the subject left the clinic and to provide assistance in management of events.

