7.5. MISSING DATA

All AEs, unless occurring during an OLFC, real world peanut challenge (RWPC), or DBPCFC, with partial/missing dates and times will be considered TEAEs unless a partial date clearly indicates that it occurred prior to first dose of AR101 in ARC008 or more than 30 days after the last dose of treatment. All therapies with partial or missing dates and times recorded on the Concomitant Medication or Non-Drug Therapy CRF pages will be considered concomitant unless a partial stop date and time clearly indicates it was stopped prior to the first dose of AR101 including parent studies. Start and stop dates will be imputed, to determine TEAEs and concomitant medications, as described below. No imputation will be done for a completely missing stop date or for subjects who did not receive study treatment.

Start dates with a missing day but which have month and year populated will be imputed such that:

- For TEAEs, if the provided month and year match the month and year for that subject's date of first dose of AR101 in ARC008, then the Day 1 date will be used
- For concomitant medications, if the provided month and year match the month and year for that subject's date of first dose of AR101 including parent studies, then the date of first dose of AR101 including parent studies will be used
- In all other cases the 1st of the month will be used with the provided month and year

Start dates with a missing day and month but which have year populated will be imputed such that:

- For TEAEs, if the provided year matches the year for that subject's date of first dose of AR101 in ARC008, then the date of first dose of AR101 in ARC008 will be used
- For concomitant medications, if the provided year matches the year for that subject's date of first dose of AR101 including parent studies, then the date of first dose of AR101 in including parent studies will be used
- In all other cases the 1st of January will be used with the provided year

For TEAEs, start dates that are completely missing will be imputed as the date of first dose of AR101 in ARC008 (Day 1). For concomitant medications, start dates that are completely missing will be imputed as the date of first dose of AR101 including parent studies.

Stop dates will be imputed as follows:

• Missing day with a provided year and month will use the last day of the month

• Missing day and month with provided year will use December 31

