9.2.1. Anaphylaxis

Anaphylactic AEs will be considered AEIs. Anaphylaxis is defined by a number of signs and symptoms that occur alone or in combination within minutes up to a few hours after exposure to a provoking agent. The severity of the reaction will be assessed according to the EAACI system for grading the severity of anaphylactic reactions (Muraro, 2007).

All reported anaphylactic reaction episodes will be listed by treatment pathway and subject.

Each anaphylactic reaction will be identified by the following triggers:

• Study product/Investigational product (IP)

- Peanut or peanut-containing food
- Other food allergen
- Medication
- Insect sting
- Environmental allergen(s)
- Other
- Unknown

Treatment-emergent anaphylactic reactions include anaphylactic reactions that occur after first dose of AR101 in ARC008 through 30 days after last dose of study product, but excluding anaphylactic reactions that occur during or related to a food challenge. Treatment-emergent anaphylactic reactions will be summarized in the Safety Population separately for the following study periods:

- Initial Escalation
- Up-Dosing
- Initial and Extended Maintenance
- Overall (Initial Escalation, Up-Dosing, and Initial and Extended Maintenance)

Summaries of each study period will include:

- The number of anaphylactic reactions.
- The number of anaphylactic reactions by trigger, study product, peanut or peanutcontaining food, other food allergen, medication, insect sting, environmental allergen, other and unknown.
- Incidence of subjects experiencing an anaphylactic reaction by number of episodes, subjects experiencing an anaphylactic reaction by severity using modified EAACI guidelines, subjects experiencing an anaphylactic reaction that was a SAE, subjects experiencing an anaphylactic reaction that required epinephrine use, the location of epinephrine episodes (home or study site), and the individual symptoms involved.

The above summary will be produced for all treatment-emergent anaphylactic reactions, all treatment-emergent anaphylactic reactions by total AR101 exposure including parent studies, and for treatment-related anaphylactic reactions. Anaphylactic reactions will also be listed by treatment pathway, subject ID, and episode date.

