13. CHANGE FROM ANALYSIS PLANNED IN PROTOCOL

The raw values for the following endpoints will be included in data listings, but the change values will not be listed or summarized:

- Secondary safety endpoints
 - Change in PEF
 - Change in C-ACT and ACT score
 - Change in TNSS
- Secondary efficacy endpoints:
 - Change in tolerated dose of peanut protein
 - Changes in food allergy QoL scores as measured by FAQLQ and the FAIM questionnaire
 - Change in FAQL-PB questionnaire score
- Exploratory endpoint:
 - Change in TRACK and EASI scores

Real world peanut challenge results will be presented in data listings and used to identify TEAEs. An analysis of these data was described in a previous version of the protocol (Protocol amendment 3 / Appendix 8).

14. **REFERENCE LIST**

DunnGalvin A, de BlokFlokstra BM, Burks AW, Dubois AE, Hourihane JO. Food allergy QoL questionnaire for children aged 0-12 years: content, construct, and cross-cultural validity. Clin Exp Allergy. 2008;38(6):977-86.

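### The maintenance row of the rescue medication summary excludes only OLFC use, so treatment for real-world peanut challenge reactions dated within maintenance is counted as rescue use during maintenance dosing

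*SAP*

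**What the plan says.** SAP 3.1 lists the frequency of epinephrine use as rescue medication among the primary safety endpoints. SAP 3.2 lists epinephrine use during the food challenges as a separate secondary endpoint.

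SAP 9.12 defines rescue medication broadly: "Rescue medications are any medication used to treat individual acute allergic reactions during ARC008". Nothing in that definition sets provoked reactions aside. The summary has six rows:

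- Initial Escalation
- Up-Dosing
- "Initial and Extended Maintenance (excluding rescue medications taken as a result of an OLFC"
- OLFCs by total exposure
- "DBPCFCs (Total AR101 Exposure < 1 year; 1 to < 2 years; 2 to < 3 years" and so on
- "Overall, including all rescue medications reported on the CRF"

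The table is repeated for the subgroups in SAP 6.3: Pathways 1-3, Pathways 4-5, daily dosing and non-daily dosing.

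The RWPC appears elsewhere. The partial-date rule in SAP 7.5 begins "All AEs, unless occurring during an OLFC, real world peanut challenge (RWPC), or DBPCFC". SAP 13 states: "Real world peanut challenge results will be presented in data listings and used to identify TEAEs", and adds that an analysis of these data was described under protocol amendment 3.

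SAP Table 4 ends the Initial and Extended Maintenance period, for every pathway, at the date of the last dose.

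**The concern.** The rows of 9.12 are where the two epinephrine endpoints are separated. SAP Section 10 sets out no epinephrine table of its own, so the challenge rows carry the secondary endpoint and the period rows carry the primary one. If a provoked reaction lands in a period row, it is read as a reaction that occurred under ordinary maintenance dosing.

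The OLFC exclusion shows that the authors wanted provoked reactions out of the maintenance row. Naming one challenge where the SAP recognises three leaves that separation incomplete.

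At stake is the maintenance-period rate of rescue medication and epinephrine use, overall and in the four subgroups. If RWPC uptake differed between pathways or dosing regimens, part of any apparent difference in rescue use would reflect who was challenged. These comparisons are descriptive only, but they will be read.

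**Working it through.** The study is descriptive and the plan states no figure to reproduce. The check is to follow each type of challenge through the stated rules.

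**OLFC.** It takes place inside Extended Maintenance. It is excluded by name from the maintenance row and has its own row. It is counted once, in the right place, and in Overall.

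**RWPC.**
1. Treatment of an RWPC reaction is treatment of an acute allergic reaction during ARC008, so it meets the 9.12 definition.
2. Table 4 assigns period by date. A use dated after up-dosing (or, in Pathways 1 and 4, from the first ARC008 dose) and no later than the last dose lies in maintenance.
3. The only exclusion from that row is for the OLFC, and there is no RWPC row.
4. The use is therefore counted in Initial and Extended Maintenance and in Overall, and nowhere else.

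Whether RWPCs were done during maintenance is not stated. It is likely: the RWPC analysis belongs to protocol amendment 3, whereas the synopsis ties the observation period after stopping AR101 to Amendment 6.0.

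9.12 counts a subject once per generic drug name and once per ATC level 4 class. So, for a given drug:

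0 ≤ subjects wrongly added to the maintenance row ≤ subjects given that drug for an RWPC reaction during maintenance.

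A subject with other maintenance use of the same drug adds nothing. The upper limit has no value in the documents.

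**DBPCFC.** It has its own row but is not named in the maintenance exclusion, so what matters is whether a dose follows the peanut challenge day. Protocol 7.1.3 says AR101 is not given on DBPCFC days and that "AR101 dosing will continue until the last food challenge is performed". Sections 7.2.5, 7.4.3 and 7.5.6 say the same. Section 7.3.6 (Pathway 3) says dosing continues until after the last challenge.

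Call the first challenge day 0 and the second day g. A use falls in maintenance if its day is no later than the last-dose day. The gaps are assumptions; the supplied text does not give the spacing. Under the Protocol 7.1.3 rule, daily dosing between challenge days is assumed. Under the Protocol 7.3.6 rule for Pathway 3, a dose on day g + 1 is assumed.

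| Protocol rule on dosing | g | Last-dose day | Peanut on first day: in maintenance? | Peanut on second day: in maintenance? |
|---|---|---|---|---|
| Until last challenge | 1 | -1 | No | No |
| Until last challenge | 2 | 1 | Yes | No |
| Until last challenge | 3 | 2 | Yes | No |
| Until last challenge | 7 | 6 | Yes | No |
| Until after last challenge (Pathway 3) | 1, 2, 3, 7 | 2, 3, 4, 8 | Yes | Yes |

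So DBPCFC use can be counted in both rows, but only under non-consecutive days with the peanut day first, or under the Pathway 3 rule read as dosing after the second day.

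**The case against.** The strongest reply concerns the DBPCFC. Unlike the OLFC, it comes at End of Treatment or about 12 months after the last dose, AR101 is withheld on its days, and it has its own row. Naming only the OLFC is then coherent. Every pathway's End of Treatment list also places the return of unused AR101 before the DBPCFC, which argues against later dosing. This largely stands: the DBPCFC overlap is a possibility, not a demonstrated count.

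A reader might infer that the SAP excludes all three challenges when identifying TEAEs, so that the rescue table will not reconcile with the TEAE and anaphylaxis tables. The documents do not support that. SAP 7.5 is a rule for partial or missing dates, not the TEAE definition. The anaphylaxis rule works by "excluding anaphylactic reactions that occur during or related to a food challenge", and where the SAP spells out food challenge (the missing-severity rule in 7.5, and 10.2) it lists the OLFC and DBPCFC only. SAP 13 says RWPC results help identify TEAEs without saying that reactions are removed. RWPC reactions may be in those tables too.

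It is also fair that other outputs bear on epinephrine: TEAEs associated with its use (9.1), the AEI summary (9.2), anaphylaxis requiring it (9.2.1) and the subject listings. They limit the damage but do not correct the maintenance row. Finally, the documents show no CRF field linking medication to an RWPC. That affects the effort needed, not the defect.

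**Conclusion.** The point holds for the RWPC. Applied as written, 9.12 counts any rescue medication for an RWPC reaction dated within maintenance as rescue use during maintenance dosing. This affects a primary safety endpoint and all four subgroup repeats, and the error can only be upward.

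The size is unknown. RWPC numbers, timing, reaction rates and epinephrine use are not in the documents, and any subject count would rest on invented inputs. If no RWPC reaction was treated during maintenance, the effect is zero. The conclusion rests on one inference, that RWPCs were done before the last dose.

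For the DBPCFC the conclusion is conditional: use can fall in the maintenance row only if a dose follows the peanut challenge day. The stronger claims, that DBPCFC use is in fact counted there and that the safety tables must disagree, go beyond the text. This is a low-cost correction that should be made, not a threat to the study's conclusions.

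**What to change.** In SAP 9.12, extend the exclusion in the Initial and Extended Maintenance row to rescue medication taken because of an OLFC, RWPC or DBPCFC. Add an RWPC row beside the OLFC and DBPCFC rows. State that challenge rows and period rows are mutually exclusive, and apply this to the subgroup repeats. Leave the Overall row unchanged, since it includes all use by design.

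Attribute each use by its cause, as the OLFC exclusion already does. If no field links medication to an RWPC, state the matching rule used, for example RWPC date plus recorded indication.

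Reconcile Protocol 7.3.6 with 7.1.3, 7.2.5, 7.4.3 and 7.5.6 on dosing around the DBPCFC, and report which reading the data follow.

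The cost is a short text change, a programming flag and a rerun of one table with its subgroup repeats. No new data collection is needed if the existing records identify RWPC-related use. Per SAP 1.1, Version 2 was prepared after database lock and is restricted to Appendix A, so the change should be documented in the CSR as made after lock.
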